[Redacted text line]

[Redacted text line]

[Redacted text block]

1. **Statement of Purpose:** State the scientific aim(s) of the study, or the hypotheses to be tested.

The aim of this study is to examine the effect of mHealth tools on antiretroviral (ART) adherence and persistence among HIV-infected individuals with co-occurring cocaine use disorders (CUDs). The specific aims are:

- (1) To conduct qualitative assessments using focus groups of people living with HIV (PLH) who use cocaine and healthcare providers that will assess the acceptability, feasibility, facilitators and barriers of implementing mHealth interventions; and will aid in developing the final design and content of both automated and clinician feedback in preparation for designing a pilot feasibility study.
- (2) To conduct a 12-week pilot feasibility RCT among PLH with co-occurring CUDs that will examine the impact of mHealth tools (cellular-enabled smart pill boxes and cell phones) and feedback (no feedback vs. automated feedback vs. automated + clinician feedback vs. vs. automated + text-reminder from a social network) on primary (ART adherence and persistence) and secondary outcomes (HIV viral suppression, cocaine use, retention in HIV care).

The hypotheses include:

- (1) Patients with automated feedback + clinician feedback will have higher ART adherence and persistence than patients with only automated feedback and patients with no feedback.
- (2) Patients with automated feedback + clinician feedback will have improved HIV outcomes including lower changes in log₁₀ HIV-1 RNA levels, higher CD4 counts and higher rates of retention in care, compared to patients with only automated feedback and patients with no feedback.
- (3) Patients with automated feedback + clinician feedback will have decreased cocaine use compared to patients with only automated feedback and patients with no feedback.
- (4) Patients with automated feedback + text-reminder from a social network will have higher ART adherence and persistence than patients with only automated feedback and patients with no feedback.
- (5) Patients with automated feedback + text-reminder from a social network will have improved HIV outcomes including lower changes in log₁₀ HIV-1 RNA levels, higher CD4 counts and higher rates of retention in care, compared to patients with only automated feedback and patients with no feedback.

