- (6) Patients with automated feedback + text-reminder from a social network will have decreased cocaine use compared to patients with only automated feedback and patients with no feedback.
- (7) There is statistically significant difference between a patient's ART adherence and persistence and HIV outcomes when their designated social network member lives inside vs outside patient's activity space.

2. **Background:** Describe the background information that led to the plan for this project. Provide references to support the expectation of obtaining useful scientific data.

Antiretroviral therapy (ART) is extremely effective at reducing morbidity and mortality, and reducing HIV transmission among people living with HIV (PLH).^{1,2} Clinical effectiveness, however, is largely dependent on patients' ART adherence and persistence.³⁻⁹ ART non-adherence and non-persistence substantially reduce viral suppression (VS)¹⁰ and increase HIV transmission risk to others.¹¹⁻¹⁵ Substance use disorders (SUDs) further contribute to poor health outcomes, primarily by reducing ART adherence and persistence.¹⁶⁻²⁰ Cocaine use disorders (CUDs), in particular, result in a number of poor HIV treatment outcomes, including decreased retention in care, poor ART adherence and persistence, low VS, and accelerated HIV progression.²¹⁻²⁸ Considering the high prevalence of CUDs among PLH²⁹⁻³⁴ and the absence of effective medication-assisted therapies (MAT) for treating CUDs, innovative strategies of improving ART adherence in this group are urgently needed.

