3. **Research Plan:** Summarize the study design and research procedures using non-technical language that can be readily understood by someone outside the discipline. **Be sure to distinguish between standard of care vs. research procedures when applicable, and include any flowcharts of visits specifying their individual times and lengths.** Describe the setting in which the research will take place.

There are two specific aims within this study. In the first specific aim, we will conduct four focus groups of people living with HIV (PLH) with co-occurring cocaine use disorders (CUDs), and two focus groups of healthcare providers to assess the acceptability, feasibility, facilitators and barriers of implementing mHealth interventions. In the second aim of the study, we will conduct a pilot feasibility RCT among PLH with co-occurring CUDs to examine the effect of mHealth tools (blister pack and cell phones) and feedback loops (no feedback vs. automated feedback vs. automated + clinician feedback vs. automated + text-reminder from a designated social network member) to assess improvement in antiretroviral (ART) adherence and persistence and other HIV health outcomes.

Specific Aim 1: *To conduct qualitative assessments using focus groups (FGs), among HIV+ cocaine users and among healthcare providers, that will assess the acceptability, feasibility, facilitators and barriers of implementing mHealth interventions; and will aid in developing the final design and content of both automated and clinician feedback in preparation for designing a pilot feasibility study.*

An initial set of 4 focus groups (FGs) comprised of 6-8 persons with HIV+ cocaine users and lasting one hour each will be conducted. Recruitment, screening, enrollment and other procedures for these FGs are discussed below. A second set of two FGs will be conducted among healthcare providers including physicians, nurses, clinic supervisors, and substance abuse counselors from HIV clinics.

Eligibility Criteria for Focus Groups of HIV-infected Cocaine Users:

- Age \geq 18 years old
- HIV+
- Current cocaine use (in the past 30 days)
- Able to speak English or Spanish
- Able to provide informed consent

Eligibility Criteria for Focus Groups of Healthcare Providers:

- Currently employed as community-based HIV physician, clinician, healthcare worker, clinic supervisor or substance abuse counselor
- Speaks English or Spanish
- Able to give informed consent

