| 
 • Age \geq 18 years • Clinic-confirmed HIV diagnosis • Currently prescribed or eligible for ART • Currently has insurance • Self-reported cocaine use ever • Willing and able to use a cell phone and blister pack for the 12-week intervention | 
 • Unable to provide informed consent • Verbally or physically threatening to research staff • Unable to communicate in either English or Spanish |
|---|--|

2.C. Informed Consent and Enrollment Procedures: All participants must be able to provide informed consent to be enrolled in the study. The RA will obtain informed consent and then explain the purposes, protocol, expectations, and possible risks and benefits of the study.

2.D. Randomization: Although a specific randomization process is not required for pilot RCTs, we want to ensure that crucial covariates that might influence our outcomes are controlled for a priori, especially given the modest sample size proposed in this pilot. Since it has been well-documented that individuals with underlying mental illness experience worse outcomes, we will minimally stratify based on the presence or absence of neurocognitive impairment. Randomization will be 1:1:1:1 to patients receiving either no feedback, automated feedback or automated + clinician feedback, and automated feedback + text-reminder from a social network.

2.E. Study Procedures:

1. Baseline Interview: After the informed consent procedure, participants will be asked to sign a medical release of information (ROI) to allow research staff to confirm self-reports of HIV status, medication prescription and healthcare utilization and to be able to communicate with the participants' clinical providers. The RA will then conduct the baseline interview consisting of various self-reported measures including demographic information, health care status, medical history, standardized measures for drug use and mental illness, and Information Motivation Behavioral (IMB) constructs for adherence. Participants will also undergo phlebotomy.

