After the 12-week intervention, all participants will be followed for a 4-week period and primary and secondary outcomes will also be recorded during the post-intervention follow-up period.

3. Monthly Research Interviews: Monthly interviews will take place for the 16-week duration of the study (12-week intervention and 4-week follow-up) for all participants. The interviews will include health care utilization, phlebotomy, self-reports of drug use, and mental illness. All phlebotomy information obtained after community release will be obtained through Quest Diagnostics, a national reference laboratory. We have a prearranged system for phlebotomy, reporting of results and storing specimens at -70C that has been in place for the past decade. None of the assays used are experimental and will be drawn as part of clinical care at standardized times as outlined. Tests will include HIV-1 RNA testing (Amplicor 1.5, range 50 to 750,000 copies/mL) and CD4 lymphocyte count using flow cytometry at baseline, end of intervention (12 weeks) and end of follow-up period (16 weeks). HIV genotypic mutations will be assessed at baseline and at 16 weeks (if VL>500 copies/mL).

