1. Risks Associated with Standardized Assessments: The standardized assessments administered during baseline and monthly research interviews will include: (1) demographic information, including age, race, and gender; (2) health care status, including past medical history, current medications, (3) standardized screening for mental illness using the Center for Epidemiologic Studies Depression Scale (CES-D);¹²¹ (4) standardized measures of drug use, including determination of DSM-V criteria for cocaine use disorder;¹²² (5) Addiction Severity Index (ASI)-Lite to assess cocaine use, polysubstance use and severity;^{123,124} (6) LifeWindows questionnaire to measure the Information-Motivation-Behavioral constructs of adherence;^{111,125} (7) ART adherence using blister pack, Visual Analog Scale (VAS) and brief adherence scale;^{126,127} (8) change in cocaine use using the Timeline Follow-Back (TLFB);¹²⁸ (9) AUDIT-C to assess alcohol use;¹²⁹ (10) health literacy;¹³⁰ (11) social support;¹³¹ (12) trust in physicians;¹³² (13) acceptance of smart pill box and smartphones;¹³³ and (14) perceived source credibility¹³⁴, (15) neighborhood delineation using the Activity Space; and (16) mapping and interpreting social or personal networks using a egocentric social network analysis questionnaire. It is possible that participants may feel uncomfortable answering these questions; in this case, they will be able to refuse answering any questions that they do not wish to answer.

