Aim 2 (Pilot Feasibility Study): The primary outcomes will be ART adherence and persistence, measured as a composite score ranging from 0 to 100%, and as number of continuous days taking ART without a 7-day (or 3-day) gap^{18,71} respectively. Outcome analyses will be conducted for (a) adherence and persistence behavior, (b) drug outcomes (cocaine use), (c) HIV treatment outcomes (VL<20 copies/mL; change in CD4+ T lymphocytes), and (d) ART-related Information, Motivation, and Behavioral Skills constructs. The general framework for discerning differences between study conditions on main outcome variables will be to perform 3 (intervention condition) x 3 (repeated follow-up assessments) mixed design analysis entering pre-intervention scores as covariates and additional theoretically and empirically relevant covariates (such as baseline mental status etc.). For variables that are approximately normally distributed, we will use multivariate analyses of covariance (MANCOVA), with significant multivariate tests followed by subsequent analyses of co-variance (ANCOVA). Variables that violate distributional assumptions of normality will be analyzed using generalized linear model (GLM) procedures, which enable the use of non-Gaussian error models. Based on a review of the literature, GLM is the most appropriate approach for variables with strong positive skew, e.g., adherence.

[figure not shown]
To examine the mediating and moderating effects of activity space and social network facilitators and barriers on primary (ART adherence and persistence) and secondary outcomes (HIV viral suppression, cocaine use, retention in HIV care), the following steps are going to be followed:

- a. A range of variables associated to activity space and social networks (both risk and support) will be calculated using a combination of GIS, SNA, and spatial statistics methods. The variables will be the covariates.
- b. The outcome variables are: primary (ART adherence and persistence) and secondary outcomes (HIV viral suppression, cocaine use, retention in HIV care).
- c. We will first use descriptive statistics, bivariate correlation, and t-tests to understand the distribution and association of all the covariates calculated in step#a with the outcome variables (step#b).
- d. After running tests of multicollinearity, only uncorrelated covariates at $p \leq 0.05$ (considered statistically significant) will be included in the subsequent mediation and moderation analysis.

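### The between-arm analysis has a three-level condition factor, but four arms are randomised and hypotheses 1 to 6 need four contrasts that no single three-level fit can supply

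*Combined protocol and SAP*

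**What the plan says.** The general framework for Aim 2 in Section 12 is "to perform 3 (intervention condition) x 3 (repeated follow-up assessments) mixed design analysis entering pre-intervention scores as covariates". MANCOVA followed by ANCOVA, or a generalised linear model for non-normal variables, is the means of carrying it out.

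The design elsewhere has four arms. The Research Plan (item 3) compares "no feedback vs. automated feedback vs. automated + clinician feedback vs. automated + text-reminder from a designated social network member". Section 2.D says "Randomization will be 1:1:1:1 to patients receiving either no feedback, automated feedback or automated + clinician feedback", and the same sentence goes on to name the social-network arm. Sample Size and Power Calculations plans 20 participants in each of groups A, B and C and 30 in group D.

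The Statement of Purpose gives the fourth arm its own hypotheses. Hypothesis 4 is that "Patients with automated feedback + text-reminder from a social network will have higher ART adherence and persistence than patients with only automated feedback", and hypothesis 6 is that "Patients with automated feedback + text-reminder from a social network will have decreased cocaine use compared to patients with only automated feedback". Hypothesis 5 makes the same comparison for HIV outcomes. All three also compare with no feedback.

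On timing, Section 2.E.3 says "Monthly interviews will take place for the 16-week duration of the study (12-week intervention and 4-week follow-up) for all participants", and the schedule table marks interviews at weeks 4, 8, 12 and 16. The text just before Section 2.E.3 says that "primary and secondary outcomes will also be recorded during the post-intervention follow-up period".

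**The concern.** Section 12 is the only place that says how arms will be compared, and its factor has one level too few. The plan does not say how four arms become three levels, so a reader cannot tell which of hypotheses 1 to 6 the analysis will test, or in which participants. Making that choice after data are in hand would weaken the stated directional hypotheses.

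A smaller question concerns the time factor. Baseline scores are covariates, so the three assessments must be post-baseline, but Section 12 does not name them. Whether data from after the intervention enter the comparison is therefore left open.

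**Working it through.** **Arm sizes.** 20 + 20 + 20 + 30 = 90, which reproduces the stated total. (Equal allocation of 90 would give 90/4 = 22.5 per arm. That is a separate mismatch; both statements describe four arms.)

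**Labels.** Section 2.E.2 identifies C as the clinician-feedback group and D as the social-network group. A as no feedback and B as automated only are inferred from the order in which the arms are listed. Exchanging A and B changes nothing below.

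**Contrasts needed.**
- Hypotheses 1 to 3: C−A and C−B.
- Hypotheses 4 to 6: D−A and D−B.

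**Independent comparisons.** D−B = (D−A) − (C−A) + (C−B), so one of the four follows from the other three. The remaining three are independent, and the set has rank 3.

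**What a three-level factor gives.** Three level means yield 3 − 1 = 2 independent differences. Since 2 < 3, no single three-level fit can estimate all four contrasts. Two examples:
- A, B and C only: C−A and C−B are estimated, and D−A and D−B are lost. The fit uses 60 participants and omits 30 of 90 (33%).
- A and B pooled: C and D are each compared with a mixed comparator, and none of the four contrasts is estimated as stated. No section describes pooling.

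**What would work.**
- A four-level factor has 4 − 1 = 3 degrees of freedom for arm, and all four contrasts are estimable. With three follow-ups the arm-by-time test has 3 × 2 = 6 degrees of freedom, against 2 × 2 = 4 as written.
- Two separate fits, A/B/C (C−A, C−B) and A/B/D (D−A, D−B), also recover all four. The plan does not mention them.

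**Is D compared anywhere else?** The mediation and moderation steps in Section 12 concern activity-space and social-network covariates and name no arm contrast. Hypothesis 7 concerns where the designated network member lives. Section 11 mentions monitoring efficacy differences and an interim analysis but gives no model. The answer is no.

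**Post-baseline assessments by outcome.**
- Interview measures: weeks 4, 8 and 12 during the intervention (three), plus week 16 (four in all).
- Adherence: Section 12 defines a composite score from 0 to 100% without its components or timing. Section 9 says "The standardized assessments administered during baseline and monthly research interviews will include" adherence by blister pack, visual analogue scale and a brief scale. Section VIII, Data Sources, instead derives adherence from weekly blister-pack photographs.
- Persistence: a count of continuous days. Section 12 does not say whether it is counted once or per assessment.
- Viral load and CD4: weeks 12 and 16 in Section 2.E.3 and the schedule table (two draws); week 12 only in Section VIII, Laboratory Measurements (one draw).

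**The case against.** The strongest reply is that this is a slip of one number. Section 12 offers a general framework rather than a final model statement. The aims, randomisation and group sizes all treat D as a separate arm, and D is the largest. A statistician would probably read the 3 as a 4. The likelihood of a slip stands, but the sentence says three, and the correction decides which hypotheses are tested. The plan should not depend on a guess.

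A second reply is that the time factor is not contradicted: weeks 4, 8 and 12 are exactly three interviews and fit interview measures naturally. That stands. What remains is a request to say so, and to say whether week 16 enters.

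A third concerns the laboratory outcomes. A reader might infer that the 3 × 3 analysis of viral load and CD4 is impossible on the stated schedule. The documents support this only conditionally. Section 12 applies the framework to main outcome variables without listing them, treats viral load as a threshold and CD4 as a change, and allows other models for non-normal data.

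Finally, this is a pilot with no power claim, and Section 11 says no efficacy difference is anticipated. That limits the weight of the point. It does not remove it, because the pilot states directional between-arm hypotheses.

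**Conclusion.** The point holds for the condition factor. As written, the framework has 2 degrees of freedom for arm where hypotheses 1 to 6 need 3, and no other section supplies D−A or D−B. The conclusion assumes that Section 12 describes one fit; two three-level fits would escape it but are not stated.

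A reader might go further and infer that the fourth arm will be left out of the analysis, or that hypotheses 4 to 6 will go untested. The documents do not say that. They leave the mapping of arms to levels open, and the A/B/C fit with 30 of 90 participants omitted is one possible reading.

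The time points are missing detail rather than an error, and the laboratory point applies only if three follow-ups are meant for those outcomes. Overall this is a specification error that should be fixed, not a threat to the trial.

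**What to change.** In Section 12, replace the three-level condition factor with a four-level arm factor (A, B, C, D; 3 degrees of freedom), define the letters, and name C−A, C−B, D−A and D−B as the contrasts for hypotheses 1 to 6. If two fits, A/B/C and A/B/D, are what is meant, state that instead.

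As a secondary clarification, list the post-baseline assessments for each outcome and say whether week 16 enters. For adherence, give the components and timing of the composite score. For persistence, give the counting window. If the three-follow-up layout is meant for viral load and CD4, reconcile Section 2.E.3 and the schedule table with Section VIII, Laboratory Measurements, and set the number of time levels to the draws actually planned.

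The arm and time-point changes cost only wording, with no new participants or data. Reconciling the laboratory schedule means settling which of the two stated schedules applies.

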Aim 1 (Focus Groups): We will conduct six FGs, four with HIV+ cocaine users and two with healthcare providers, comprised of 6-8 persons each. For the PLH FGs, we will recruit PLH who primarily use cocaine, from clinical care and community outreach programs in New Haven, CT. Of the four PLH FGs, one will consist solely of men and one solely of women in order to address possible gender differences. Eligibility criteria will be: a) ≥ 18 years; (b) speaks English or Spanish; c) HIV+; d) self-reported cocaine use in the previous 30 days; and e) able to give informed consent. For the two healthcare provider FGs, we will recruit physicians, nurses, clinic supervisors, and substance abuse counselors from HIV clinics. We will target representation from the 5 HIV clinics in New Haven.

Aim 2 (Pilot Feasibility Study): We will recruit 90 participants from HIV care clinics and drug treatment programs in New Haven. Eligibility criteria will include: 1) clinic-confirmed HIV diagnosis; 2) ≥ 18 years; 3) prescribed or eligible (clinician willing to prescribe) for ART; 4) currently have insurance coverage; 5) self-reported cocaine use in the past 6 months; and 6) and willing and able to use an electronic pill box and blister pack for study duration. This will be a 16-week study with a 12-week intervention and 4-week post-intervention observation period.

Sample Size and Power Calculations: The literature suggests that effect size calculations may not be appropriate for pilot RCTs.¹¹⁵ Thus, based on a review of pilot studies that have ranged in sample size from 12 per group¹¹⁶⁻¹¹⁸ to 9%-50%^{119,120} of the proposed larger RCT's sample size (generally 30 per arm); we propose to enroll 20 participants for groups A, B, and C. For Group D, we propose to enroll 30 participants so that hypotheses #7 (There is statistically significant difference between a patient's ART adherence and persistence and HIV outcomes when their designated social network member lives inside vs outside patient's activity space) can be tested. Therefore, a total of 90 study participants for the pilot feasibility RCT is proposed. This sample size is appropriate in order to refine study procedures, develop a final intervention manual and prepare for a future large-scale RCT.

NOTE: Is this research proposal designed to enroll children who are wards of the state as potential subjects? Yes No (If yes, see Instructions section VII #4 for further requirements)

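### For approximately normal outcomes, the planned MANCOVA drops anyone missing one modelled follow-up, and no missing-data method is stated

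*Combined protocol and SAP*

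**What the plan says.** Item 12, Statistical Considerations (Aim 2), sets out a "3 (intervention condition) x 3 (repeated follow-up assessments) mixed design analysis entering pre-intervention scores as covariates". It then splits the outcomes by distribution:

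- Approximately normal variables: "we will use multivariate analyses of covariance (MANCOVA), with significant multivariate tests followed by subsequent analyses of co-variance (ANCOVA".
- The rest: "Variables that violate distributional assumptions of normality will be analyzed using generalized linear model (GLM) procedures". Adherence is given as the example: "GLM is the most appropriate approach for variables with strong positive skew, e.g., adherence".

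On arm sizes, the sample size paragraph under item 5 (Subject Population) says "we propose to enroll 20 participants for groups A, B, and C" and "For Group D, we propose to enroll 30 participants".

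The Background says that cocaine use disorders "result in a number of poor HIV treatment outcomes, including decreased retention in care". Specific Aim 2 in the Research Plan lists retention in the trial as a secondary outcome.

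The document contains no rule for missing data, no imputation method, no intention-to-treat statement, and no expected dropout or retention rate.

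**The concern.** Standard MANCOVA needs the full outcome vector for each participant. A person with two of three follow-ups contributes nothing to the multivariate test. The ANCOVAs follow only if that test is significant, so running them visit by visit does not undo the selection: the complete-case test decides whether they are run at all.

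Two things are at stake for the outcomes on this route.

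- **Precision.** Three of the four arms have only 20 participants.
- **Bias.** It arises if the people who miss visits differ in outcome, or differ by arm, in ways the covariates do not capture. The protocol gives some reason to take this seriously. Hypotheses 2 and 5 predict better retention in care in the two enhanced-feedback arms, and the Monthly Research Interviews paragraph says the blood tests are drawn within clinical care, so the availability of laboratory data could differ by arm. The Risks section also lets participants decline any question, which adds item-level gaps.

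The study is meant to inform a larger trial, so means and variances taken from completers alone could mislead that design.

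**Working it through.** **The plan's own figure.** 3 × 20 + 30 = 90, which agrees with the stated total. There is no power, dropout or complete-case figure to reproduce.

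**Inputs.**
- Modelled follow-ups: 3 (item 12).
- CD4 follow-ups: 2, at weeks 12 and 16 (Monthly Research Interviews and the schedule table). The Laboratory Measurements paragraph in Section VIII lists CD4 at baseline and week 12 only.
- Arm sizes: 20, 20, 20 and 30.
- Missingness per visit, m: not in the document. Assumed 10% to 20%.

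**Independent misses.** Share excluded = 1 − (1 − m)^k for k follow-ups.

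| Follow-ups modelled | m = 10% | m = 20% |
|---|---|---|
| 3 (item 12 model) | 1 − 0.729 = 27.1%; 20 becomes 14.6, 30 becomes 21.9 | 1 − 0.512 = 48.8%; 20 becomes 10.2, 30 becomes 15.4 |
| 2 (CD4) | 1 − 0.810 = 19.0%; 20 becomes 16.2 | 1 − 0.640 = 36.0%; 20 becomes 12.8 |

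At m = 5% and three follow-ups, the loss is 1 − 0.95³ = 14.3% (20 becomes 17.1).

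**Clustered misses, three follow-ups.** In a threshold model with equally correlated normal variables, correlation 0.5 gives 21.8% at m = 10% and 38.9% at m = 20%. Correlation 0.9 gives 15.0% and 27.8%. Under pure dropout, where nobody who leaves returns, the loss is simply the share gone by the last visit.

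**Precision.** Detectable standardised difference between two arms, assuming 80% power and two-sided 5%: (1.960 + 0.842) × √(2/n).
- n = 20: 0.89
- n = 14.6: 1.04
- n = 10.2: 1.24

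The plan claims no power, so these figures only show the scale of the loss.

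**What a method using partial follow-up keeps.** The share with at least one of three follow-ups is 1 − m³: 99.9% at m = 10% and 99.2% at m = 20%, against 72.9% and 51.2% complete.

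**The case against.** A reader might infer three stronger things. The document supports none of them.

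**That the trial will lose a quarter to a half of each arm.** Over three visits, that range needs about 9% to 21% independent missingness per visit, and the document gives no rate. The Background sentence concerns retention in HIV care, not attendance at trial visits. The one remark on study retention, about an earlier study of 48 patients with substance use disorders, calls it high without giving a figure. Misses may well cluster, which reduces the loss.

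**That the randomised comparison is broken.** Complete-case analysis biases the comparison only if missingness depends on outcome or arm beyond the covariates, and the plan already enters baseline scores. Dependence is plausible, but the document does not show it. Otherwise the cost is mainly precision.

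**That the primary adherence result is affected.** Adherence is assigned to GLM and viral load below 20 copies/mL is binary, so MANCOVA is left with whichever other variables prove roughly normal, such as the IMB scores and CD4 change. The lost pillbox data of 8 participants concern adherence and so lie outside this step.

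Other points are fair. CD4 has at most two follow-ups; if only week 12 is used, the multi-visit mechanism disappears for it. The text does not make clear whether the multivariate test runs over visits, over several outcomes, or both, though each version needs complete vectors. This is a pilot that claims no power.

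What stands is the default to complete cases, its role in deciding whether ANCOVAs are run, and the absence of any stated way to handle gaps.

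**Conclusion.** The point holds within limits. For the approximately normal outcomes, the planned multivariate test excludes anyone with an incomplete set of modelled assessments, and nothing in the plan offsets this. Every size given here rests on assumed missingness: 27% to 49% excluded over three follow-ups at 10% to 20% independent missingness per visit, 22% to 39% at correlation 0.5, and 19% to 36% over two CD4 follow-ups. Lower or more clustered missingness gives less. Loss of precision follows directly from any exclusion. Bias is conditional on the missingness mechanism.

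This is a cheap improvement to the plan, not a defect in its primary adherence analysis.

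**What to change.** In item 12, replace MANCOVA/ANCOVA with a likelihood-based linear mixed model for repeated measures, fitted to all observed assessments. Its terms would be arm, visit, arm-by-visit, baseline value and the randomisation stratum. Arm should have four levels to match the four randomised arms; item 12 currently plans a "3 (intervention condition) x 3 (repeated follow-up assessments) mixed design analysis". With arms this small, specify a degrees-of-freedom correction such as Kenward-Roger. For repeated non-normal outcomes, specify a mixed GLM. Unweighted GEE needs a stronger missingness assumption and would not remove the bias described. The same edit should say which assessments enter the model for each outcome, because the schedule has monthly interviews at weeks 4, 8, 12 and 16 but fewer laboratory follow-ups.

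The cost is a short text change and standard software, with no new data. There is a small downside: the model relies on data being missing at random, so it can still be biased if people miss visits because of their unobserved current state, and it needs the small-sample correction. With complete data, it gives nearly the same answer as the planned analysis.
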